### **4.2. Protocol deviations**

The analysis population will be intention to treat, and will include all participants enrolled and randomized. Adherence to protocol will be determined during the 14-day assessment based on patient report of whether they took the medication delivered by the trial. At that time, the trial will assess whether patients have taken other medication during the study period, including azithromycin or other macrolides not provided by the trial. Patients who take azithromycin or other macrolide not provided by the study will be considered protocol deviations but will be included according to randomized group in the intention-to-treat analysis.

## **5. Trial Population**

### **5.1. Screening data**

We will report the number of patients screened and characteristics to the extent they are available to assess representativeness of the enrolled study population.

### **5.2. Eligibility**

See Section 4 of the trial protocol for eligibility criteria.

### **5.3. Recruitment**

See section 5.1 of the study protocol. We will report the number of participants screened, enrolled, randomized, and measured at the primary endpoint, along with reasons for exclusion at each step following CONSORT guidelines.

### **5.4. Withdrawal/follow-up**

We will report the proportion of patients in both study arms who withdraw from the trial, along with reasons. We will report this information in the trial's CONSORT flow chart. The analysis will be intention-to-treat: patients will be analyzed according to the arm they are randomized.

### **5.5. Baseline patient characteristics**

We will summarize patient characteristics by arm, including: age, sex, location (to level of US state), and clinical symptoms at the time of enrollment.

## 6. Analysis

### 6.1. Outcome definitions

#### Primary Outcome:

The primary outcome will be free of symptoms at 14 days after the electronic enrollment assessment. Symptoms include: cough, fever, myalgia, anosmia, shortness of breath (and related abilities such as ability to walk across a room or up a flight of stairs), fatigue, conjunctivitis, and orthostatic symptoms.

#### Secondary Outcomes:

- **Hospitalization and/or death by 14 days** after the electronic enrollment assessment.
- **Hospitalization/death by 21 days:** we will extend follow-up beyond the primary endpoint to capture any hospitalizations or death that progress more slowly and are not detected by 14 days.
- **Adverse events:** we will conduct an adverse event survey at Day 3 after treatment, including gastrointestinal side effects (nausea, vomiting, diarrhea, abdominal pain) and rash. We note that some COVID-19 patients report gastrointestinal symptoms, and this survey will provide data on whether azithromycin causes additional gastrointestinal effects beyond those symptoms.
- **Prevalence of positive swabs:** we will compare the prevalence of SARS-CoV-2 positive swabs at Day 3 after treatment in self-collected nasal, saliva, and rectal swabs in azithromycin compared to placebo-treated participants.
- **Viral load:** we will assess viral load by RT-PCR in self-collected nasal, saliva, and rectal swabs at Day 3 after treatment.
- **Mortality:** we will collect emergency contact/next of kin information during the baseline questionnaire. We will follow-up with the emergency contact if participants are lost to follow-up at the Day 14 and Day 21 questionnaires to assess mortality and hospitalization outcomes.
- **Genetic macrolide resistance determinants:** We will evaluate the prevalence of genetic macrolide resistance determinants *ermB*, *mefA/E*, and *mphA* by targeted PCR in rectal samples collected at Day 3 after treatment.
- **COVID-19 symptoms at 21 days:** we will ask patients about COVID-19 symptomology during each online questionnaire, including cough, fever, myalgia, anosmia, shortness of breath (and related abilities such as ability to walk across a room or up a flight of stairs), fatigue, conjunctivitis, and orthostatic symptoms.
- **Number of emergency room visits:** during each online questionnaire we will survey patients about any emergency room visits (with stays <24 hours) that occurred since their last survey.
- **Number of household members with COVID-19 (confirmed or symptomatic):** during each online questionnaire we will ask participants how many of their household members have symptoms of COVID-19 or confirmed disease.

### 6.2. Analysis methods

#### Primary Outcome:

The primary analysis will estimate the risk difference (RD) comparing the proportion of patients who are symptom-free at 14 days in the azithromycin versus placebo arms. We will compute *P*-

values for differences between arms using a permutation test with the prevalence difference between arms as the test statistic and 10,000 iterations. We will additionally estimate and report the prevalence ratio.

Determination of statistical significance for the primary and secondary analyses will follow the final alpha-spending function determined by the interim analyses (see section 3.5).

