3.5 Sample Size

The COVID-19 epidemic is changing rapidly over time. We propose a group sequential design with a flexible sample size that is adaptive to changing trial parameters over time with no maximum sample size. These designs are used in outbreak trials due to uncertainty with respect to parameters such as incidence and severity of outcomes. Full details on the sample size are provided in the Statistical Analysis Plan. In brief, the trial will employ a committee that is masked to results by arm that will evaluate the sample size on a weekly basis to evaluate the sample size based on the probability of hospitalization and enrollment.

On December 2, 2020 the DSMC members agreed to revise the sample size and primary outcome of the trial. Our re-estimated sample size of N=455 would allow for detection of a 15% absolute difference in probability of being symptom free at 14 days assuming that 50% in the placebo arm are symptom free (this is based on the current overall percent of participants who are symptom free at 14 days in ACTION). Because ACTION is enrolling more slowly than we had anticipated and we are planning a smaller sample size and we are also planning a single interim analysis at approximately 50% enrollment (N=230 participants), testing for efficacy at $p=0.001$, and then assess the final outcome at $p=0.049$.

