### 3.3. Sample size

The trial's revised target enrollment is 455 participants, which will be sufficient to detect an increase in the proportion of patients who are symptom free 50% to 65% (15 percentage point increase) at 14 days from enrollment.

With 455 participants, the trial will have 80% power to detect an increase of 15 percentage points in the percentage of patients who are symptom free at 14-d under the following assumptions:

- 2:1 allocation ratio of azithromycin : placebo
- 50% symptom-free under placebo at the 14-day measurement (binomial outcome)
- 20% loss to follow-up
- 2-sided alpha of 0.05, power = 0.8.

- A single interim analysis with 50% of primary outcomes collected with stopping guideline determined using the Lan-DeMets spending function approach with an O'Brien and Fleming boundary.

The table below shows sample sizes under several effect size scenarios, assuming azithromycin increases the proportion of patients who are symptom free by 0.1 to 0.2 compared to placebo.

Sample size required for a fixed design allowing for 20% loss to follow-up. Calculations assume 2-sided alpha of 0.05 and 80% power.

p placebo	p azithro	RD	N placebo	N azithro	N Total
0.5	0.60	0.10	348	695	1,043
0.5	0.61	0.11	287	573	860
0.5	0.62	0.12	240	479	719
0.5	0.63	0.13	204	407	611
0.5	0.64	0.14	175	349	524
0.5	0.65	0.15	152	303	455
0.5	0.66	0.16	133	265	398
0.5	0.67	0.17	117	233	350
0.5	0.68	0.18	104	207	311
0.5	0.69	0.19	93	185	278
0.5	0.70	0.20	83	165	248

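### The 80% power in SAP 3.3 is a Z-test figure with too little allowance for loss; with 364 evaluable, the planned permutation test has about 76%, or 78% if it redraws arm sizes

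*SAP*

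**What the plan says.** SAP 3.3 claims: "With 455 participants, the trial will have 80% power to detect an increase of 15 percentage points". The listed assumptions are "50% symptom-free under placebo at the 14-day measurement (binomial outcome", "2:1 allocation ratio of azithromycin : placebo", "20% loss to follow-up" and "2-sided alpha of 0.05, power = 0.8", with one interim look under a Lan-DeMets O'Brien-Fleming boundary. The table beside them is labelled as a fixed design and splits 455 into 152 placebo and 303 azithromycin.

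SAP 6.2 makes the primary P-value a "permutation test with the prevalence difference between arms as the test statistic and 10,000 iterations". Protocol section 9 also plans a permutation test with 10,000 iterations. Neither document says whether arm sizes are held fixed when labels are permuted, or how a two-sided P-value is formed. Neither gives a power for this test. SAP 3.2 says that randomization is neither stratified nor blocked.

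For the test levels, Protocol 3.5 plans "testing for efficacy at $p=0.001$, and then assess the final outcome at $p=0.049". SAP 3.5 gives one-sided nominal values of 0.0015 (Z = 2.96) at the interim and 0.0245 (Z = 1.97) at the end.

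**The concern.** The sample size was justified with one test and the trial will be decided by another. With a binary outcome and fixed arm sizes, the difference in proportions takes only a limited set of values, so a permutation test cannot use its whole nominal level and loses some power to a Z test. Separately, the allowance for loss looks too small. Together these would make the 80% in SAP 3.3 too high for the trial as planned. The sample size had already been cut because enrolment was slow, so the figure should describe what the design delivers. A lesser matter is that a P-value simulated from 10,000 draws could make a close interim decision depend on the random seed.

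**Working it through.** **1. Reproduce 455.** The inputs from SAP 3.3 are 0.50 on placebo, 0.65 on azithromycin, 2:1 allocation, two-sided 0.05 and 80% power. The mean rate is (0.50 + 2 × 0.65)/3 = 0.60. Without continuity correction:

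n(placebo) = [1.960 × √(0.60 × 0.40 × 1.5) + 0.8416 × √(0.25 + 0.2275/2)]² / 0.15²
= [1.1760 + 0.5076]² / 0.0225 = 125.97.

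The total is 3 × 125.97 = 377.9 evaluable.

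- Multiplied by 1.2: 453.5. Rounding each arm up gives 152 + 303 = 455, the SAP's figure. The other ten table rows also match this rule within 2 patients.
- Divided by 0.8: 472.4, so 473. This does not match.
- With continuity correction: 490 or 510. Neither matches.

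**2. What the stated loss leaves.** 455 × 0.8 = 364 evaluable. The multiplier 1.2 instead protects 455/1.2 = 379, which corresponds to a loss of 1 − 379/455 = 16.7%.

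**3. Z-test power at 364.** With 364/3 = 121.33 on placebo, power = Φ[(0.15 × √121.33 − z × 0.6)/0.6031]:

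- z = 1.960 (level 0.05): Φ(0.790) = 78.5%.
- z = 1.969 (level 0.049): Φ(0.781) = 78.3%. Full enumeration over the unblocked arm sizes gives 78.2%.

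**4. Permutation test with arm sizes held fixed.** Given T symptom-free participants among N, the number in the placebo arm is hypergeometric. The two-sided P-value sums the probabilities of all tables whose absolute difference is at least the one observed. Power is the binomial probability of all outcomes with P ≤ 0.049, averaged over the arm sizes that unblocked 2:1 randomization produces:

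| Evaluable | Z test | Permutation, two-sided on absolute difference | Permutation, one tail against 0.0245 |
|---|---|---|---|
| 364 | 78.2% | 76.4% | 74.6% |
| 379 | 79.8% | 78.2% | 76.4% |

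The true size of the two-sided version is about 0.043.

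**5. Permutation test with arm sizes redrawn.** If each label is redrawn independently with probability 1/3 for placebo, the arm sizes vary and the steps become much finer. Power at 364 is then 78.1%, in effect the same as the Z test.

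**6. Split the shortfall (two-sided, fixed arms).**

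- 80.0% to 79.8%: final level 0.049 instead of 0.05, at 379 evaluable.
- 79.8% to 78.2%: 364 evaluable instead of 379, 1.6 points.
- 78.2% to 76.4%: permutation instead of Z, 1.8 points (1.6 at 379).

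The interim look hardly matters. With two looks and final arms of 121 and 243, power is 76.4% for the permutation test and 78.6% for the Z test.

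**7. Enrolment for 80% with the fixed-arm test.** About 390 to 400 evaluable are needed (79.3% and 80.3% at level 0.049). Divided by 0.8, that is 488 to 500 enrolled.

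**8. Simulation noise.** The standard error of a P-value of 0.001 from 10,000 draws is √(0.001 × 0.999/10,000) = 0.00032, or 32% of the threshold. At a two-sided 0.003, which is twice the SAP's 0.0015, it is 0.00055, or 18%. A true P of 0.0012 would show as 0.001 or less in about 35% of runs. Such near-threshold results are uncommon: at a 0.001 interim look, simulated and exact decisions differ in 1.0% to 1.6% of trials under the design effect and about 0.02% under the null.

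**The case against.** The strongest reply is that planning with a normal approximation and analysing by permutation is a modest mismatch, and that its error in size is on the safe side. The test itself costs under 2 points on the reading that matches the stated two-sided level. It costs about nothing if the permutation follows the unblocked randomization, which the SAP's wording allows. All of this stands, and it is why the point is minor. It does not rescue the 80%: with 364 evaluable, no reading checked exceeds about 78%.

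Three stronger readings are tempting but not supported:

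- A reader might infer that the permutation test alone takes power from 80% to 76%. About half of that gap arises before any choice of test, from multiplying by 1.2.
- A reader might infer that 10,000 draws damage the trial's power or error rate. They do not: at arms of 121 and 243, simulated and enumerated power agree (76.6% against 76.5%). The noise matters only for a P-value very near the interim threshold.
- A reader might infer that a mid-P version would recover the lost power free of charge. It brings power at 364 back to about 78%, but its true size exceeds 0.049 at some arm splits: 0.0513 at 245/119, 0.0539 at 243/136 and 0.0549 at 268/111. It is a trade-off and is not recommended here.

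**Conclusion.** The point holds and is minor. The 80% in SAP 3.3 is a pooled-Z figure for about 379 evaluable participants. Under the SAP's own 20% loss, power at the final 0.049 level is about 78% for a Z test. For the permutation test it is about 76% with arm sizes fixed and a two-sided P on the absolute difference, and about 78% with arm sizes redrawn. If one tail were compared with 0.0245, it would be about 75%. There are two causes of similar size, the loss multiplier and, on the fixed-arm reading, the test.

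These figures assume true rates of 50% and 65%, a loss of exactly 20% unrelated to outcome, and 2:1 allocation without blocking. They do not show that the primary test is invalid; with fixed arms it is slightly conservative.

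**What to change.** - **SAP 6.2:** state that the P-value is two-sided, how it is formed (for example, on the absolute difference), and whether permutation holds arm sizes fixed or redraws them.
- **SAP 3.3:** restate the power for that test with 364 evaluable: about 76% with fixed arms, or about 78% if arm sizes are redrawn. Name both causes: loss was allowed for by multiplying by 1.2 instead of dividing by 0.8, and power was computed for a Z test.
- **Computation:** with fixed arms, compute the P-value exactly from the hypergeometric distribution, or use many more than 10,000 draws, so that a close interim result does not depend on the seed. State the interim threshold once, since Protocol 3.5 (0.001) and SAP 3.5 (0.0015 one-sided) differ.

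The cost is a few sentences and a few lines of code, and no extra participants. Keeping 80% with the fixed-arm test would instead need about 490 to 500 enrolled.

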### **Secondary Outcomes:**

- **Hospitalization/death by 21 days:** We will use a Kaplan-Meier approach to account for losses to follow-up. We will use Greenwood's formula to estimate the standard error of the log proportion in each arm will be used to determine the variance of the risk difference at 21 days.
- **Mortality by 21 days:** we will collect emergency contact/next of kin information during the baseline questionnaire. We will follow-up with the emergency contact if participants are lost to follow-up at the Day 14 and Day 21 questionnaires to assess mortality and hospitalization outcomes.
- **COVID-19 symptoms at 21 days:** we will ask patients about COVID-19 symptomology during each online questionnaire, including cough, fever, myalgia, anosmia, shortness of breath (and related abilities such as ability to walk across a room or up a flight of stairs), fatigue, conjunctivitis, and orthostatic symptoms.
- **COVID-19 (confirmed or symptomatic) among household members of enrolled patients:** during each online questionnaire we will ask participants how many of their household members have symptoms of COVID-19 or confirmed disease. This analysis will be conducted on an expanded dataset that includes an observation for each household member. To account for outcome correlation among individuals within households, we will estimate 95% confidence intervals for the risk difference and risk ratio with a clustered, non-parametric bootstrap that resamples households with replacement (10,000 iterations).

### *Outcomes with a prevalent measure at Day 3:*

We will estimate the difference in prevalence between arms and the 95% confidence interval for the difference. We will compute *P*-values for differences between arms using a permutation test with the prevalence difference between arms as the test statistic and 10,000 iterations.

- **Prevalence of positive swabs:** we will compare the prevalence of SARS-CoV-2 positive swabs at Day 3 after treatment in self-collected nasal, saliva, and rectal swabs in azithromycin compared to placebo-treated participants.
- **Genetic macrolide resistance determinants:** We will evaluate the prevalence of genetic macrolide resistance determinants *ermB*, *mefA/E*, and *mphA* by targeted PCR in rectal samples collected at Day 3 after treatment.
- **Adverse events:** we will conduct an adverse event survey at Day 3 after treatment, including gastrointestinal side effects (nausea, vomiting, diarrhea, abdominal pain) and rash. We note that some COVID-19 patients report gastrointestinal symptoms, and this survey will provide data on whether azithromycin causes additional gastrointestinal effects beyond those symptoms. We also note that adverse events will be cumulative through Day 3 and measure cumulative incidence (risk) not prevalence.

### *Outcomes with a continuous measure at Day 3:*

We will compare log transformed values of relative read and number of reads using a t-test. We will compute *P*-values for differences between arms using a permutation test with the difference between arms as the test statistic and 10,000 iterations.

- **Viral load:** we will assess viral load by RT-PCR in self-collected nasal, saliva, and rectal swabs at Day 3 after treatment.

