9. On top of the ULINE shipping box, remove or black out the old shipping label.
10. Take the new shipping label, provided with the kit and fill out your **NAME, ADDRESS, AND PHONE NUMBER** under the **FROM** section (Section 1). Be sure to press hard with a ballpoint pen. Everything else on the shipping label will be filled out for you.
11. Remove the top sheet of the shipping label to keep for your records. There should be two sheets remaining on the shipping label. **Do not remove the FedEx copy.**
12. Flip the label over and peel the backing off of the label. The back of the label should be sticky.
13. Stick the new label over the old label. Press down firmly on all corners to make sure it sticks.
14. Proceed to the shipping instructions to send your samples back to UCSF.

Shipping Instructions:

There are two ways to ship your samples back to UCSF. Each are described below:

1. Coordinator Assisted Shipping
 - a. Contact the **UCSF study coordinators** at **[contact]** or **[contact]**
 - b. The coordinators will take down your information and schedule a pickup at your house. Prepare to receive another call for further information about your samples' pick up.
2. Self-Schedule Shipping
 - a. Call **FedEx** at **[name]**
 - b. Say "schedule pick-up".
 - c. Say "I don't have an account number, use tracking number"
 - d. Continue scheduling a time that works for you. When you are finished, leave your package outside your door.
The total process should take five to ten minutes. If you are uncomfortable with this method please call the study coordinators instead as mentioned above.

7 Laboratory Procedures

All laboratory processing will be done at the conclusion of the trial. Samples will be de-identified. All laboratory personnel will be masked and samples will be processed in a randomized fashion.

Nasal swabs are placed in Zymo, which inactivated all infectious agents, including SARS-CoV-2. RNA will be extracted and subjected to RT-PCR to detect the E gene of SARS-CoV-2.

E Gene Primers and Probes

| | Sequence (5' to 3') |
|------------------|----------------------------|
| SARS-CoV-2 E Fwd | ACAGGTACGTTAATAGTTAATAGCGT |
| SARS-CoV-2 E Rev | ATATTGCAGCAGTACGCACACA |

| Probe | Sequence (5' to 3') |
|-----------------------|----------------------------|
| SARS-CoV-2_E_Prpb-FAM | ACACTAGCCATCCTTACTGCGCTTCG |

8 Duties and Responsibilities of Staff

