8.6 Laboratory Technicians

- Prepare patient study kits with all materials needed for the study
- Organize study supplies
- Prepare patient information sheets and swab instructions
- Scan swabs received from the participants into the REDCap database
- Assist with laboratory analysis of samples
- Assist with biobanking and storage of specimens

9 Statistical Methods

Please see the Statistical Analysis Plan for details on pre-specified statistical methods for this trial.

The primary analysis will estimate the risk difference (RD) and risk ratio (RR) comparing azithromycin to placebo. We will estimate these parameters using a logistic regression model with a single covariate for treatment arm. We will estimate the RD and RR from the logistic regression using marginal standardization, and a bootstrap for 95% confidence intervals [5,6]. We will compute *P*-values for differences between arms using a permutation test with the difference between arms as the test statistic and 10,000 iterations.

The secondary analysis of viral load will compare log transformed values of relative read and number of reads using a t-test. We will compute *P*-values for differences between arms using a permutation test with the difference between arms as the test statistic and 10,000 iterations.

Determination of statistical significance for the primary and secondary analysis will follow the final alpha-spending function determined by the group sequential design.

10 Study Medication

The study drug product will be obtained from Pfizer, Inc. Participants enrolled in the study will be offered a dose of oral azithromycin or placebo determined by their randomization allocation. We will monitor adverse events following treatment as described in Chapter 9.

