## **6.3. Missing data**

If outcome data are missing for >15% of participants we will report results from sensitivity analyses for missing data [4,5]. We selected 15% missing because trials with >20% missing values are thought to be a concern for bias [6]. The primary analysis will account for censoring but will assume outcomes are missing completely at random. We will relax this assumption slightly, assuming that outcomes are missing at random (MAR) with an inverse-probability weighted (IPW) estimator using cumulative incidence through 14 days as the binary endpoint. We will model the probability of censoring as a function of baseline patient characteristics with a logistic regression model, and will use the inverse of the predicted probabilities from the model to re-weight the analysis population to reflect the full study population at the time of enrollment, using a doubly-robust targeted maximum likelihood estimator that also includes an outcome model using the same covariates [7]. Baseline characteristics used in the censoring model will include age, sex, race/ethnicity, zip code, comorbidities, concomitant medications, symptoms at enrollment, insurance status, alcohol use, tobacco/e-cigarette/marijuana use, and household composition. We will additionally consider a range of scenarios assuming the outcomes are missing not at random (MNAR), *i.e.* systematically, using a pattern mixture model approach described by Little et al. [4], whereby we model cumulative incidence through 14 days with a linear probability model as a function of covariates listed for the IPW estimator; missing outcomes will then be imputed using the model fit to predict, adding a shift parameter  $\Delta$  that we vary across a range of values.

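### The viral-load analysis is written for sequencing reads although the assay is RT-PCR, and it has no rule for undetected swabs

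*SAP*

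**What the plan says.** SAP 6.1 defines the outcome by its assay: "we will assess viral load by RT-PCR in self-collected nasal, saliva, and rectal swabs at Day 3 after treatment". Protocol 3.4.2 matches it.

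Protocol 7 (Laboratory Procedures) gives the method in a paragraph that opens with nasal swabs: "RNA will be extracted and subjected to RT-PCR to detect the E gene of SARS-CoV-2". It lists two primers and a probe. No sequencing step for viral load is described in either document.

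The analysis text uses a different quantity. SAP 6.2, under continuous Day 3 measures: "We will compare log transformed values of relative read and number of reads using a t-test". Protocol 9: "The secondary analysis of viral load will compare log transformed values of relative read and number of reads using a t-test". P-values are to be computed "using a permutation test with the difference between arms as the test statistic and 10,000 iterations".

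Positivity is a separate Day 3 outcome in SAP 6.2: "we will compare the prevalence of SARS-CoV-2 positive swabs at Day 3 after treatment in self-collected nasal, saliva, and rectal swabs".

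The missing-data section (SAP 6.3) begins "If outcome data are missing for >15% of participants we will report results from sensitivity analyses for missing data" and goes on to methods for a missing 14-day endpoint. It does not mention zeros, undetected results or a detection limit.

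**The concern.** There are two gaps. First, read counts come from sequencing. A probe-based RT-PCR gives a cycle threshold (Ct), or a copy number if a standard curve is run. The relative-read term is never defined, and nothing says how a PCR result becomes the analysis variable. The wording is in the current SAP (version 6) as well as the appended version 5, so it is not just superseded text.

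Second, some Day 3 swabs will be negative. If a negative is stored as zero, its log does not exist; if Ct is used, a negative has no Ct. Either way the analyst must choose a rule that the plan does not give. The easiest course, letting such swabs fall out, compares only participants who still have detectable virus. That set is determined after randomization and may differ by arm if the drug works.

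At stake is the size of the viral-load difference, and whether it can be read as a randomized comparison.

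**Working it through.** **Plan's own figure.** There is none to reproduce. The documents give no SD, mean, detection limit, positivity rate or power for viral load.

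**Can the stated analysis take a negative?** log(0) is minus infinity. One such value makes the arm mean infinite and the t statistic and its P-value undefined (computed result: NaN). The permutation statistic is a difference in means of the same logs, so it fails for the same reason.

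**Effect of dropping undetected swabs.** All inputs are assumed: log10 load normal with SD s = 2, placebo mean 4.0, azithromycin mean 3.5 (true difference -0.50), detection limit L = 2. The mean among detected swabs is m + s·φ(a)/[1 − Φ(a)], with a = (L − m)/s.

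- Placebo: a = −1.00; φ = 0.2420; proportion detected = 0.8413; mean = 4 + 2 × 0.2420/0.8413 = 4.575.
- Azithromycin: a = −0.75; φ = 0.3011; proportion detected = 0.7734; mean = 3.5 + 2 × 0.3011/0.7734 = 4.279.
- Difference = 4.279 − 4.575 = −0.296. Loss = 1 − 0.296/0.50, about 41%.
- Dropped: about 16% of placebo and 23% of azithromycin swabs.

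**Range.** With the true difference held at −0.50 and placebo mean varied over 4 to 6, SD over 1 to 3 and limit over 1 to 3:

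- Mean 6, SD 1, limit 1: almost nothing is undetected, and the loss is about 0%.
- Mean 4, SD 3, limit 3: means among detected swabs are 5.795 and 5.585, a difference of about −0.21 and a loss of about 58%.

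**Setting undetected values at the limit** (worked example): p × detected mean + (1 − p) × 2, where p is the proportion detected, gives 4.167 on placebo and 3.762 on azithromycin. The difference is about −0.40, still short of −0.50 but closer than −0.30.

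**Does the choice of rule matter to the test?** Illustrative simulation with 4,000 replicates and a t-test at two-sided 0.05. Arm sizes are 243 and 121, from 455 × 0.8 = 364 split 2:1. This is an upper bound, since it supposes that every followed participant gave a swab. Log10 copies in positives are normal, with mean 5 on placebo and SD 1.5. Scenarios: (a) 40% negative on placebo and 50% on azithromycin, no difference among positives; (b) 40% negative in both arms, 0.5 log10 lower among positives; (c) 10% negative in both arms, same 0.5 reduction.

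| Rule for negatives | (a) rejection | (b) power | (c) power |
|---|---|---|---|
| Dropped | 5% | 63% | 82% |
| Set to 50 copies | 33% | 30% | 68% |
| log10(x + 1) | 38% | 19% | 54% |
| log10(x + 0.001) | 42% | 11% | 34% |

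The same data give very different answers under different rules, and no rule in the table is best throughout.

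**The case against.** The strongest reply is that reads may be loose or carried-over wording for a PCR quantity. The first gap would then be a labelling error that the laboratory could resolve. That is fair, and for that reason a reader should not infer that viral load cannot be analysed at all; RT-PCR data can be. But the quantity would still be unnamed and undetected swabs would still have no rule.

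A reader might also infer that dropping negatives would hide viral clearance from the trial. The documents do not support that: SAP 6.2 compares Day 3 positivity between arms with its own permutation test. Nor does a negative swab prove clearance. In the swab scheme of Protocol 3.3 only Group 1 gives a Day 0 sample, and only nasal, so a negative saliva or rectal swab may never have been positive.

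A reader might quote the 41% loss as the expected bias. It is one assumed point in a range from about 0% to 58%.

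It can also be said that keeping negatives is not always better. This stands. In scenario (b) a rank-sum test has about 20% power against about 63% when negatives are dropped. In the worked example the order reverses: 56% to 58% against 35% to 36% in repeated simulation. The right rule depends on the effect to be estimated, which is why it has to be chosen in advance.

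**Conclusion.** The point holds. In the current text of both documents the stated viral-load variable does not match the RT-PCR assay, and the log-scale mean difference is undefined for undetected swabs, which the plan itself expects. These conclusions rest on the wording alone. The size of the consequence rests on assumed distributions: dropping undetected swabs attenuates a true −0.5 log10 difference by about 0% to 58%, and by 41% (to −0.30) at mean 4, SD 2 and limit 2.

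The scope is one secondary outcome on opt-in swabs with no power claim attached. Nothing here touches the symptom-free primary analysis or N=455. It should be corrected, but it does not threaten the trial's main conclusion.

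**What to change.** In SAP 6.2 and Protocol 9, replace the read-based wording with the RT-PCR quantity the laboratory will report: Ct, or log10 copies if a standard curve is run. State in Protocol 7 whether the same assay applies to saliva and rectal swabs.

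Keep every analysable swab. Before unmasking, specify one rule that treats undetected swabs as the lowest viral load. On the Ct scale that means the highest Ct, because a lower Ct means more virus. Two suitable choices are a rank statistic in the permutation test already planned, or a left-censored model at the detection limit. If a mean difference with undetected values set at the limit is also shown, label it descriptive, since it still attenuates (about −0.40 against −0.50 in the example).

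Cost: wording in two documents and no new samples. Reporting copies would also need a standard curve, which Protocol 7 does not describe. Protocol 7 places laboratory processing at the end of the trial, so the rule can be fixed before results exist. The downside is power: a rank or substitution rule can lose to dropping negatives when clearance is equal in both arms.
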